4.4.2.4 Binary Endpoints (Incidences)

The proportion of patients experiencing the event will be presented for each of the two treatment groups. This will apply to the patients still shedding virus per planned visit, all secondary illnesses endpoints, and hospitalisations (for viral shedding it will be presented by treatment group, age cohort and flu type).

- Incidence of any secondary illnesses: each patient can have several LRTCs, therefore a table of frequencies of 0 to 4 LRTC will be obtained per treatment arm.
- Incidence of secondary illnesses for patients treated with antibiotics: as above, the frequency of LRTC will be obtained by treatment arm.
- Incidence of initiation of treatment with antibiotics: The probability of antibiotic use will be compared between treatment arms using probability differences and confidence intervals of those differences.
- Incidence of hospitalisations: probabilities of hospitalisation per treatment arm and their CI's will be provided.
- Duration of hospitalisation: given that there may be few hospitalisations, this subgroup analysis will only report median times and ranges by treatment arm.

4.4.3 Exploratory Efficacy Endpoints

Descriptive statistics may be used to further investigate symptom scoring in adults and children considering that symptoms of the patient's underlying immune status and baseline conditions could overlap with influenza-like illness symptoms in this patient population.

4.4.4 Sensitivity Analyses

4.4.4.1 Efficacy Analyses using ITTi

All analyses relating to TTR of all symptoms and TTR of individual symptoms, described in Section 4.4.2.1, will be repeated using the ITTi population.

4.4.4.2 Efficacy Analyses excluding other antiviral patient data

The TTR (mITTi) of all symptoms analyses described in Section 4.4.2.1 will be rerun excluding any follow-up data collected from those patients who began treatment with another antiviral for influenza, on or after discontinuation of study drug. Note that although Section 8.2.7.1 of the protocol indicates that such exclusions should be made for all efficacy analyses, this statement contradicts the definition of the ITT, ITTi and mITTi populations, so the exclusions of antiviral patient data will be regarded as a sensitivity analysis rather than the main analysis. Non-immunocompromised patients will be excluded.

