4.1.1 Intent To Treat (ITT) Population

All patients randomized will be included in the ITT population. Patients will be summarized under the treatment to which they were randomized. This population may be used to summarize efficacy endpoints for the purpose of sensitivity analyses. This population will generate the most conservative effect estimates because there may be allocation errors, non-infected patients and/or non-adherence to treatment.

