4.1.3 Modified Intent To Treat infected (mITT_i) Population

All patients randomized to a particular treatment, regardless of whether they received that treatment or not, and received at least one dose of study drug and with central laboratory confirmation of influenza infection, excluding patients infected with oseltamivir-resistant influenza at baseline, will be included in the mITT_i population. This population will also be used to summarize all efficacy and resistance endpoints because it will render least biased effect estimates. This population was not defined in the protocol.

The definition of oseltamivir-resistant influenza at baseline is defined in Section 2.2.6. Decisions on patient exclusion from the ITT, ITT_i and mITT_i population sets will be made by the statistician and study scientist after database closure. Excluded patients will be documented along with the reason for exclusion.

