4.1.6 Protocol Deviations

Major protocol deviations will be listed in the CSR. Major protocol deviations will include those captured during the study conduct (██████ file), as well as any additional deviations found as a result of programmatic checks of the following criteria:

- Patients who received their first study drug dose more than 96 hours from onset of symptoms.
- Patients with randomization errors – randomized and not dosed, dosed prior to randomization.
- Use of antiviral treatment for influenza in the 2 weeks prior to randomization and during the 10 day treatment phase of the study.
- Less than 16 of the 20 planned doses (80%) of study drug.

Sensitivity analyses may be carried out excluding any major protocol deviations.

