4.4.2.2 Comparison of TTR of All Symptoms to Historical Control

It is unethical to treat IC patients with placebo. Nevertheless, it is important to ascertain whether treating IC patients for influenza is still better than not treating them. Given the ethical constraint, the next best possible comparison available is against historical placebo controls. Thus, any difference between these two groups will be due to both IC status (yes/no) and oseltamivir effect. It will not be possible to differentiate both effects statistically. Historical controls will come first and foremost from pivotal historical oseltamivir studies where otherwise healthy (OwH) were enrolled. The main comparison of active treatment with historical control placebo will be based on a 1:1 matching of all adult NV20234 patients with OwH placebo patients from the pivotal studies. All patients in the adult mITTi population will be matched to historical patients (from the pivotal studies) that received a placebo.

There are three types of matches in order of priority:

1. Patients will be matched 1:1 within viral strain and then by age with ± 5 years caliper (the lowest limit being 18) and gender. Any remaining unmatched individual will be matched by age and gender alone. Only

pivotal studies will be used. Outputs in [appendix 5](#) refer to this matching rule.

2. Patients will be strictly matched 1:1 by age as above, gender and influenza strain. Only pivotal studies will be used. There will probably leave more unmatched patients but those matched will be more similar than in 1.
3. Patients will be matched 1:>1 as in 1 above using pivotal and non-pivotal but relevant historical studies. Additional matching by time between symptoms onset and first treatment (possibly with a caliper) will be used if closer matching is required. This is a sensitivity analysis captured in section [4.4.4](#).

In cases where those matching rules are not sufficient, i.e. more than one patient in the 1:1 placebo matching, an additional rule will be the elapsed time from first symptoms to first dose. If several matches are still available in the 1:1 ratio, one match will be chosen at random (the seed of the random number generator will be kept for reproducibility).

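### Section 4.4.4.2 removes non-immunocompromised patients as well as post-antiviral data, so it cannot isolate antiviral use, and no population definition says whether such patients belong

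*SAP*

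**What the plan says.** Section 4.4.4.2 names its reference analysis: "The TTR (mITTi) of all symptoms analyses described in Section 4.4.2.1 will be rerun". The stated change is that this is "rerun excluding any follow-up data collected from those patients who began treatment with another antiviral for influenza", on or after stopping study drug. The section explains that the protocol asked for this exclusion in all efficacy analyses. Because that conflicts with the ITT, ITTi and mITTi definitions, it concludes: "so the exclusions of antiviral patient data will be regarded as a sensitivity analysis rather than the main analysis". Then follows one further sentence, with no explanation: "Non-immunocompromised patients will be excluded". The SAP states the rule nowhere else.

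The population definitions do not mention immune status. For ITT, "All patients randomized will be included in the ITT population". The mITTi population takes randomized patients who "received at least one dose of study drug and with central laboratory confirmation of influenza infection, excluding patients infected with oseltamivir-resistant influenza at baseline". Section 4.1.3 leaves exclusions from ITT, ITTi and mITTi to the statistician and study scientist once the database is closed, with reasons documented.

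The synopsis in Appendix 1 limits the target population to immunocompromised (IC) patients. Section 4.4.2.2 interprets the historical comparison accordingly: "any difference between these two groups will be due to both IC status (yes/no) and oseltamivir effect".

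**The concern.** A sensitivity analysis is useful when it changes one thing and leaves the rest alone. The only question that 4.4.4.2 sets itself is whether follow-up data after another antiviral influence TTR. If it also drops a group of patients for an unrelated reason, a change in the result has two possible sources, and so does the absence of a change.

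The same sentence raises a question about the rest of the plan. If the trial can contain non-IC patients and the plan wants to see TTR without them, it should say how they are treated in the analyses that matter more: the co-primary resistance proportion, the dose comparison of TTR and the historical comparison. The last of these is interpreted as the joint effect of IC status and oseltamivir, which presumes that every patient in this trial is IC.

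**Working it through.** No arithmetic applies. The SAP gives neither the number of non-IC patients nor the number who started another antiviral. The check sets the sections side by side.

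**1. What 4.4.4.2 can identify.** Consider four versions of the mITTi analysis of TTR of all symptoms:
- A: the main analysis (4.4.2.1).
- B: A without the post-antiviral follow-up data.
- C: A without non-IC patients.
- D: A with both exclusions.

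The plan produces A and, read as written, D. The contrast is D − A = (B − A) + (D − B). The first term is the antiviral question and the second is the effect of dropping non-IC patients. Neither B nor C is planned, so the terms cannot be separated. They coincide with the intended contrast only if no non-IC patient is in mITTi or if removing those patients has no effect.

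**2. Whether the population definitions already settle it.**

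| Population | Section | Condition on immune status | Main use |
|---|---|---|---|
| ITT | 4.1.1 | none | main TTR tables (4.4), baseline resistance (4.7) |
| ITTi | 4.1.2 | none | efficacy (4.4) |
| mITTi | 4.1.3 | none | efficacy (4.4), co-primary resistance where possible (4.7) |
| Safety | 4.1.5 | none | co-primary safety (4.6) |
| PKEP | 4.1.4 | none explicit; significant eligibility violators may be dropped | pharmacokinetics (4.5) |

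A randomized non-IC patient who meets the other conditions therefore belongs to the first four populations. PKEP is a partial exception, because its exclusion is optional.

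**3. Other routes by which such a patient could be removed.**
- Section 4.1.3 allows exclusions after database closure but gives no criterion on immune status.
- Section 4.1.6 counts as major deviations those captured during study conduct, plus programmatic checks. The checks begin with "Patients who received their first study drug dose more than 96 hours from onset of symptoms" and go on to randomization errors, other antiviral use and fewer than 16 of the 20 doses. Immune status is not among the checks, but an eligibility breach could be captured during conduct. Sensitivity analyses excluding major deviations are optional.

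**4. Whether another planned analysis answers the question.** The remaining sensitivity analyses vary the population (ITTi), the historical controls, the length of follow-up, the time to first dose and the definition of secondary illness. The subgroups in 4.4.5 are vaccination, transplant status, time to first dose, age and region. Transplant status is not a substitute: from protocol version C the trial also enrols patients without a transplant, so the non-transplant group contains IC patients too. Appendix 5 has no row for 4.4.4.2 and none restricted by immune status.

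**5. The alternative reading.** The last sentence might be a general rule in the wrong place. It would then conflict with 4.1.1 to 4.1.3, which admit such patients, and two programmers following the SAP could build different mITTi sets. The text needs correction under either reading.

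**The case against.** The strongest reply has four parts.

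**Retention is ordinary practice.** Keeping randomized but ineligible patients in an intention-to-treat set is normal, and all efficacy here is secondary or exploratory with no formal hypothesis. This stands. The point does not ask for their removal from the main analysis, only that the plan state their status and keep the two exclusions apart.

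**The plan has routes to find and remove them.** This stands in part. Section 4.1.3 allows documented exclusions, PKEP can drop eligibility violators, and 4.1.6 captures deviations during conduct. A reader might infer that non-IC patients go undetected or stay in every analysis. The SAP does not support that. It does leave removal without a criterion, and it leaves the deviation-based analysis optional.

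**Such patients may not exist.** A reader might infer from the sentence that the sponsor knows of non-IC enrolments. The SAP gives no count or expectation, and the target population is IC. If there are none, removing the sentence changes no result.

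**The numerical effect may be small.** Section 4.4.4.2 reruns the comparison of the two randomized doses. Under 1:1 allocation non-IC patients would be expected in both arms, so a shift in each arm's median would largely cancel in the dose difference. This also stands. It would be wrong to scale any effect against the 34 hours in Section 2.3, because that difference refers to active treatment versus historical placebo, not to the contrast in 4.4.4.2. The reply does not cover the medians within each arm or the historical comparison, where no such cancellation applies.

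**Conclusion.** The point holds. As written, 4.4.4.2 makes two changes to the main mITTi analysis and justifies only one, so it cannot answer its own question. Separately, the SAP does not settle whether non-IC patients belong to ITTi and mITTi. By the definitions they stay in the main efficacy, resistance and safety analyses unless removed by an exclusion decision for which no criterion is given.

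The size is unknown. Any figure would need the number of non-IC patients and their TTR relative to IC patients, and the SAP gives neither. A reader might infer that the main results are materially distorted; nothing in the document shows that. The conclusion rests on the text alone and assumes that the protocol section cited in 4.4.4.2, which was not available, does not itself supply the missing rule. Even if it did, the SAP's population definitions would need to reflect it.

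**What to change.** 1. Take the non-IC exclusion out of 4.4.4.2, so that this analysis differs from the main mITTi analysis only by the antiviral rule.
2. State in Section 4.1 whether non-IC patients belong to ITTi and mITTi. Do this together with step 1: if a general exclusion was intended, simply deleting the sentence would remove the only record of it.
3. If they stay in, commit to a separate mITTi sensitivity analysis restricted to patients who meet the IC inclusion criterion. It should cover the co-primary resistance proportion, TTR of all symptoms by dose and the 1:1 historical comparison.
4. Fix the list of non-IC patients before treatment codes are released. Section 2.4 already places the review of the population datasets at that stage.

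The cost is SAP wording and a small extra set of tables. No new data are needed, because Section 4.3 already summarises immunodeficiency conditions at baseline.

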4.4.4.3 Additional efficacy analyses using alternative historical controls

Further sensitivity analyses of TTR of all symptoms may be carried out using alternative historical control datasets as follows:

1. 1: >1 mapping with OwH patients.
2. 1: >1 mapping with At Risk patients.

The purpose of the alternative historical control datasets is two-fold:

- 1) Increase the precision on the historical median response by increasing the number of patients contributing to this sample using a 1 :> 1 mapping approach.
- 2) Provide a range of placebo responses that may be considered plausible surrogate responses for an IC untreated population. This is based on the evidence of an observed difference in placebo responses for otherwise healthy patients compared with at risk and elderly patients in the oseltamivir adult treatment database.

To allow for potential exploratory analyses of other efficacy endpoints, the historical control dataset will also include the patient level variables where readily available: baseline creatinine clearance, age, gender, virus type and subtype,

time to cessation of viral shedding, AUE of symptom scores, AUC of viral titer, time to resolution of individual symptoms.

4.4.4.4 Comparison of TTR of All Symptoms to Historical Control

The following Kaplan-Meier analyses will be carried out using the mITTi population to support the comparison of Study NV20234 treatment response with the historical placebo response with both 1:1 and 1:>1 ratios:

- The TTR of all symptoms for adults using only follow-up symptom data recorded up to and including 25 days compared with historical placebo data. This is to investigate the impact of differences in the follow-up observation periods between study NV20234 and the oseltamivir treatment database. Adult patients in Study NV20234 who have not experienced resolution of symptoms by day 25 will be censored on day 25. In the historical studies (see section 4.4.2.2 above and [appendix 4](#)) the final assessment was between days 17 and 25 post onset. A sensitivity analysis will be carried out comparing results from the previous analyses against an analysis without censoring at 25 days, i.e. using the current final assessment ~40 days after onset of symptoms.
- The TTR of all symptoms for patients who had symptoms onset ≤ 48 hours before first dose, for each active treatment group and combined, compared with matched historical control patients.

4.4.4.5 Additional Secondary Illnesses Analysis

The incidence of specified secondary illnesses summaries will be repeated, sub-setting on any LRTC starting on or after study day 3 or at least 48 hours after first study drug intake and treated with antibiotics. This should exclude pre-existing secondary illnesses that may not be linked to the treatment. These incidences will be repeated for LRTCs regardless of antibiotic use. Antibiotic use for secondary illnesses will be selected from the concomitant medications log prior to database lock. These will be identified as antibiotic treatment received for the above secondary illnesses.

4.4.5 Subgroup Analyses

To check for comparability of treatment groups across the stratification levels used to randomize the study, the TTR of All Symptoms in the mITTi population will be summarized by treatment group split by:

- Vaccination status (yes vs. no).
- Transplant status (yes vs. no).
- Time from symptom onset to time of first dose (≤ 48 hours vs. > 48 hours).
- Age (≤ 12 vs. > 12 years).

The stratification by Transplant status was added in Protocol version C.

A further subgroup analysis of TTR of All Symptoms (mITTi) will be carried out by geographical location. The 5 regions will be North America (USA and Mexico), South America (Brazil, Colombia and Guatemala), Eastern Europe (Bulgaria,

Estonia, Hungary, Latvia, Lithuania, Poland and Ukraine), Western Europe (Belgium, Italy, Spain and Israel) and South Africa. A single Kaplan-Meier analysis will be done by geographic region.

4.4.6 Additional analyses not specified in the protocol

Two additional analyses for efficacy (TTR and temperature) that were not in the original protocol have been introduced in the SAP.

4.4.6.1 Use of 90% CIs

In addition to 95% CI, 90% CI will be also shown when comparing current data against historical controls. This was agreed jointly by PDCO, CHMP and Roche in a briefing document dated [REDACTED] where the possibility of establishing a new dose recommendation/regimen was discussed.

4.4.6.2 Removal of >48 hour symptom onset to dose restriction

Although the protocol originally specified this comparison would be restricted to those patients who received treatment within 48 hours (≤ 48 hours), such analysis will be conducted as a sensitivity analysis only. The rationale for the additional analyses is that there is no direct evidence that dosing more than 48 hours after the start of symptoms will not be effective. Whilst evidence from a large observational study suggests an increased benefit for patients if dosed within 48 hours, compared with patients dosed after 48 hours, there is still evidence of benefit if dosed more than 48 hours after symptom onset. In addition, IC patients can have prolonged viral shedding compared to immune-competent patients, suggesting that administration of drug after 96 hours after symptom onset may still provide benefit to these patients by limiting duration of their influenza.

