Any patient from study NV20234 who has not been matched will not be included in these analyses. Matches will be done independently for historical placebo and historical treated. Modifications of the matching rules above may be permitted if scientifically required, e.g. matching by time in 3 above requires a window. The ITTi population in historical studies is equivalent to the current mITTi population.

The pivotal studies to be used are: WV15671 (18-65y, OwH, USA, placebo-conventional-double) and WV15670 (18-65y, OwH, Europe, Canada, Hong-Kong, placebo-conventional-double). Potential additional studies include: WV15730 (18-65y, OwH), M76001 (13-80y, OwH, placebo-conventional) and WV15758 (1-12y, OwH, placebo-conventional).

A similar comparison may be done between current IC patients and historical patients defined as at risk. There may be a 1:1 and 1:>1 matching ratios. The historical studies with patients at risk include WV15812 (≥ 13 y, placebo-conventional) and WV15872 (≥ 12 y, placebo-conventional). Additional studies in elderly (>65 years of age) are: WV15819, WV15876, WV15978 and WV15707 (see [Appendix 4](#)).

The following median differences in TTR of all symptoms (90% and 95% CIs) will be reported:

1. Comparison of conventional dose with matched placebo.
2. Comparison of double dose with matched placebo.
3. Comparison of combined conventional and double dose with combined matched historical placebo (if the results of the NV20234 dose group comparisons suggest responses are similar).

To aid interpretation of the results, the median TTR of all symptoms and associated 90% CIs will be plotted against historical placebo responses for a) NV20234 conventional dose b) NV20234 double dose c) NV20234 combined dose groups.

In addition to the comparison of NV20234 active with placebo patients from the pivotal studies, a *treatment* historical control dataset will be created from the same adult treatment studies, matching NV20234 patients randomized to the conventional dosing arm with the conventional dose from the adult treatment studies. This will enable an informal comparison of the treatment response of IC patients with the treatment response in otherwise healthy patients. Patients will be matched using the same rules as those for historical control.

The full specifications for historical control groups can be found in [Appendix 4](#). The final set of historical placebo patients will be confirmed prior to treatment unblinding and database lock.

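### Does matching all adults, rather than only those dosed within 48 hours, undermine the main historical-placebo comparison of symptom resolution?

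*SAP*

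**What the plan says.** SAP section 4.4.6.2 records the departure openly: "the protocol originally specified this comparison would be restricted to those patients who received treatment within 48 hours", but "such analysis will be conducted as a sensitivity analysis only". The Version F synopsis in Appendix 1 has the same restriction: the placebo population is to be comparable to trial patients first dosed within 48 hours.

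The main comparison is defined in section 4.4.2.2: "All patients in the adult mITTi population will be matched to historical patients". Rule 1 matches 1:1 on viral strain, then age within 5 years and gender; patients still unmatched are paired on age and gender alone. When more than one control qualifies, "an additional rule will be the elapsed time from first symptoms to first dose". A stronger use of that variable appears only in rule 3, the 1:>1 sensitivity matching: "Additional matching by time between symptoms onset and first treatment (possibly with a caliper) will be used if closer matching is required". The section adds that "Modifications of the matching rules above may be permitted if scientifically required", and that the control set is to be confirmed before unblinding and database lock.

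TTR starts at first dose (section 2.2.2.1 and Appendix 7). From Protocol Version C, patients may start up to 96 hours after onset, and 48 hours or less versus more than 48 hours is a stratification factor (sections 2 and 3.1). Section 4.4.4.4 plans the matched comparison in patients dosed within 48 hours, and Table A5.1 in Appendix 5 lists its outputs.

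**The concern.** A patient dosed at 80 hours has already passed through much of the illness before the TTR clock starts. If the matched placebo patient was dosed at 24 hours, the trial patient could resolve sooner with no drug effect at all. A tie-break cannot supply a late-starting control where none exists.

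The stated rationale does not meet this point. Section 4.4.6.2 argues that late treatment may still work, which is a reason to study late starters but not a reason to pair them with earlier-observed controls. Its last step, that "administration of drug after 96 hours after symptom onset may still provide benefit", concerns dosing that section 4.1.6 treats as a major deviation: "Patients who received their first study drug dose more than 96 hours from onset of symptoms".

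Section 4.4.2.2 uses this comparison to ask whether treating immunocompromised (IC) patients is better than not treating them. It attributes any difference to IC status and oseltamivir, and does not mention stage of illness. On that reading, the headline carries an avoidable source of non-comparability on top of one that the design cannot remove.

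**Working it through.** **1. The plan's own power figure.** Inputs from section 2.3: 75 per group, difference 34 h, SD 98 h, two-sided 10% alpha, a Wilcoxon test. Using the rank-sum efficiency 3/π:

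Power = Φ(34 / (98 × √(2 / (n × 3/π))) − 1.645)

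At n = 75: n × 3/π = 71.6; 98 × √(2/71.6) = 16.38; 34/16.38 = 2.076; Φ(0.431) = 66.7%. The plan states 66%, so the figure reproduces as a two-sample calculation.

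**2. The adult base.** The comparison is in adults only. The synopsis asks for at least 166 patients, at least 15 of them under 18, and assumes 90% confirmed infection. Assuming exactly 15 paediatric patients, split evenly, (166 − 15)/2 × 0.9 = 67.95, about 68 adults per arm. The formula then gives 63.0%.

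**3. Cost of making the within-48-hour analysis the headline.** The late share is not given, so a range is shown. The CI width ratio is √(1/(1 − late share)).

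| Late starters | n per arm | Power | CI width against all adults |
|---|---|---|---|
| 0% | 68.0 | 63% | 1.00 |
| 10% | 61.2 | 59% | 1.05 |
| 33% | 45.5 | 49% | 1.22 |
| 47% | 36.0 | 42% | 1.37 |

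**4. Possible size of the stage-of-illness shift.** Assumptions, none of them from the SAP: no drug effect, the same total illness duration in both groups, controls dosed at 6–48 h, late starters at 48–96 h, everyone still ill at first dose. Control TTR SD is held at about 98 h. The table gives the shift in median TTR (trial minus control, hours) without the tie-break; a negative value flatters active treatment.

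| Duration model | 10% late | 25% late | 50% late |
|---|---|---|---|
| Gamma, shape 0.6 | +0.4 | +1.8 | +3.7 |
| Gamma, shape 1 (constant hazard) | 0 | 0 | -0.1 |
| Gamma, shape 2 | -1.6 | -4.5 | -9.2 |
| Gamma, shape 4 | -3.6 | -9.1 | -18.5 |
| Log-normal, log-SD 0.6 | -2.6 | -6.5 | -13.2 |
| Log-normal, log-SD 1.0 | +0.9 | +2.2 | +4.5 |

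The sign depends on the hazard. The shift is negative when recovery speeds up as the illness goes on, and positive when those still ill late are mostly those with long illness.

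**5. With the tie-break.** Taking the nearest of 3 or 10 otherwise eligible controls, the shift at 10–25% late is about +2 to -6 h across all nine duration models run. At 50% late with 10 eligible controls it is about +3 to -10 h. The tie-break is only partial: late starters still enter about 28 h later than their match, against 45 h without it.

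**6. Scale.** At 10–25% late the largest shift is 6/34 = 18% of the clinically relevant difference. The extreme of -18.5 h is 54% of it (18.5/34), and needs half the patients late, the most sharply rising hazard and no working tie-break. Total illness only 1.1% to 10.6% longer in IC patients would cancel the negative shifts in the gamma models with rising hazard.

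**The case for a change.** The best case for a change is that it looks cheap and that the confounder can be removed. Section 4.4.2.2 concedes that IC status and drug effect cannot be separated, but that is a limit of the design, whereas onset-to-dose time is on the list of dataset variables in Appendix 4. Two outputs could swap labels, or a caliper could be fixed before unblinding, without new data. The ≤48/>48 hour subgroup summary in section 4.4.5 compares the dose arms without controls, so it does not address the mismatch.

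Part of this stands. The rationale in section 4.4.6.2 does not deal with stage of illness, and section 4.4.2.2 could have named it as another possible source of difference. Table A4.1 mentions only age and gender, but it also leaves out strain and the 5-year window. It is therefore a general abbreviation of the matching rules and not evidence of a decision about onset time.

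The remedies gain little. Relabelling produces the same two analyses and changes only which is called main. If the controls all started early, a caliper drops much the same patients as the 48-hour restriction, and that analysis is already planned. If the controls have a similar onset-to-dose mix, there is no shift to correct. The remark about dosing after 96 hours is part of a rationale and alters no analysis.

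**Conclusion.** The facts behind the concern are right, but the plan does not need to change. Time zero is first dose in both groups; what may differ is how far the illness had run by then. Whether it differs cannot be told from the SAP, because the historical onset-to-dose window and the late share are not stated.

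The sponsor's choice is defensible. It is disclosed in its own section and keeps a stratum that the trial was designed to enrol. It concerns a secondary endpoint reported with confidence intervals and no hypothesis test, and the restricted matched analysis stands beside it. Confirming the control set before unblinding limits outcome-driven rematching.

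Under the assumptions above, the shift is about +2 to -6 h at 10–25% late starters with the tie-break working, against 34 h. The alternative headline would answer for a narrower population at 59% to 42% power instead of about 63%. A statistician could prefer either. Showing onset-to-dose distributions for matched pairs, and reading the all-adult and within-48-hour results together, are matters of reporting that the required dataset variables and planned outputs already allow.
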